13.3 Clinical Safety Laboratory Test Data

13.3.1 Data Presentation

The PCS criteria used for the clinical safety laboratory tests can be found in Table 3.

The clinical safety laboratory test values will be presented both in conventional and Système International (SI) units.

13.3.2 Anti-Drug Antibody (ADA) including Neutralizing Antibody (NAb) assessments

Analysis of specific anti-eptinezumab antibodies is restricted to subjects who are randomized to eptinezumab.

For subjects with pre-existing antibodies at Baseline, the number and percent of subjects who are positive for anti-eptinezumab antibody will be summarized. In addition, the number and percent of subjects who develop anti-drug antibodies to eptinezumab during the trial will be summarized at each scheduled visit. Denominators for percentages will be the total number of samples taken for the specified visit. For patients with ADA, neutralizing properties of anti-eptinezumab antibodies will also be summarized.

All the immunogenicity data will be listed by period.

Subjects with a positive anti-eptinezumab antibody result will be listed by period.

For inclusion in the CSR, all the adverse events occurring before entering the Extension Period in patients with positive anti-eptinezumab antibody results in the Placebo-controlled Period or with pre-existing antibodies at Baseline, will be listed. The listing will include the ADA result, the assessment date, the preferred term for the adverse event, and start date and stop date of the adverse event. The ADA results and adverse events will be listed in chronological order according to assessment date and the start date of the adverse event.

Similar listings will be provided for patients with ADA-positive results occurring after start of V8 IMP infusion, including all the adverse events for the patients, for inclusion in the addendum to CSR.

In addition, summaries of TEAEs by SOC and preferred term will be provided for the Placebo-controlled Period and for the Extension Period for patients who are ADA-positive.

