	 Change from baseline in the number of monthly days with use of acute migraine medication Change from baseline in the number of monthly migraine days with use of acute migraine medication PGIC score Change from baseline in the number of monthly migraine days in patients with MOH MBS score Change from baseline in monthly number of Migraine attacks for each 12-week period Change from baseline in monthly number of Headache episodes for each 12-week period Change from baseline in the MSQ v2.1 sub-scores Change from baseline in the EQ-5D-5L VAS score HCRU Change from baseline in the WPAI sub-scores
 Safety Objective To evaluate the safety and tolerability of eptinezumab To evaluate the long-term safety and tolerability of eptinezumab 	 Safety Endpoints Adverse events Absolute values and changes from baseline in clinical safety laboratory test values, vital signs, weight, and ECG parameter values Potentially clinically significant clinical safety laboratory test values, vital signs, weight changes, and ECG parameter values Development of specific anti-eptinezumab antibodies (ADA) including neutralizing antibodies (NAbs) Columbia-Suicide Severity Rating Scale (C-SSRS) score

2 Study Design

This is an interventional, multi-national, multi-site, randomized, double-blind, placebocontrolled Phase IIIb study designed to demonstrate efficacy and safety of eptinezumab for migraine prevention in patients with unsuccessful prior preventive treatments. The placebocontrolled period will be followed by an extension period where all patients will receive active treatment to assess the long-term safety, tolerability and effect of eptinezumab.

The target population for this study is defined as patients with chronic migraine (CM) or episodic migraine (EM), as outlined in the IHS ICHD-3 guidelines¹ with documented evidence of migraine occurring on \geq 4 days per month prior to screening as confirmed via prospectively collected information in the eDiary during the Screening Period, and with documented evidence of failure to 2-4 different preventive migraine medications in the past 10 years. The aim is that approximately 40% of the randomized patients are patients with EM.

It is planned that 840 patients will be randomly allocated to one of three treatment groups: eptinezumab 300 mg, eptinezumab 100 mg, or placebo, in a ratio of 1:1:1.

Randomization will be stratified by country and monthly headache days (MHDs) at baseline (\leq 14 MHDs/>14 MHDs).

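### SAP 13.3.2 plans no once-per-patient incidence for the endpoint 'development of ADA'; it tabulates ADA only visit by visit, over the samples taken at that visit.

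*SAP*

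**What the plan says.** SAP Panel 1 and protocol Panel 3 list the development of ADA, including neutralizing antibodies, as a safety endpoint. SAP 13.3.2 sets out the analysis:

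- Population: "Analysis of specific anti-eptinezumab antibodies is restricted to subjects who are randomized to eptinezumab".
- Baseline: "For subjects with pre-existing antibodies at Baseline, the number and percent of subjects who are positive for anti-eptinezumab antibody will be summarized".
- After Baseline: "the number and percent of subjects who develop anti-drug antibodies to eptinezumab during the trial will be summarized at each scheduled visit".
- Percentages: "Denominators for percentages will be the total number of samples taken for the specified visit".
- Listings: "All the immunogenicity data will be listed by period", and "Subjects with a positive anti-eptinezumab antibody result will be listed by period".

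The section also plans a summary of neutralizing properties and, for each period, an adverse event table in ADA-positive patients. It does not define ADA-positive, treatment-emergent ADA or *develop*.

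Protocol Panel 2 schedules ADA blood at Baseline, at Weeks 12, 24, 36, 48, 60 and 72, and at the Withdrawal Visit, with no restriction by arm. At infusion visits it is drawn before the infusion (footnote n).

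**The concern.** An endpoint worded as development calls for a count of patients: of those who could develop ADA, how many did? The planned percentage divides subjects by one visit's samples. Its denominator includes patients positive at Baseline, who cannot newly develop ADA, and it changes from visit to visit with attendance. Nothing in the section combines visits within a patient.

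Two further gaps follow from the population rule. Placebo patients are allocated to eptinezumab at Visit 8, yet were not randomized to it at the start, so the text leaves open whether up to 280 newly exposed patients are in the Extension Period ADA analysis. And no placebo results after Baseline are shown beside the active arms.

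ADA incidence is the result a reader of the safety report will look for. If the plan does not define it, it will have to be built after unblinding from listings, under rules not fixed in advance.

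**Working it through.** The documents state no ADA rate, assay cut-point or false-positive rate, so there is no planned figure to reproduce. The check compares the texts and then bounds the effect under stated assumptions.

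**1. What the by-visit percentage can mean.** Three readings of *develop* at a visit are possible:

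| Reading | What the table gives |
|---|---|
| Positive at that visit | Visit prevalence; transient positives are not accumulated |
| Newly positive at that visit | Counts could be summed over visits, but each percentage has its own denominator |
| Positive at or before that visit | Positive patients who leave stay in the numerator but not in the denominator |

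None of the three yields a stated percentage of at-risk patients who develop ADA in a period.

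**2. The SAP's own practice elsewhere.** SAP 13.2 summarizes patients with one or more PCS values at any time after Baseline, per period, and bases safety denominators on patients with data. SAP 13.3.3 counts each patient once for the liver criteria, by group and period. SAP 13.3.2 does neither and gives no reason.

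**3. Bounds on any-time incidence.** Take the first reading, with baseline positives outside the numerator, complete sampling, and the same visit percentage p (assumed) at each of k post-baseline visits. The share ever positive is p if the same patients are positive each time, 1 − (1 − p)^k if visits are independent, and k × p if no patient is positive twice.

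| p (assumed) | k = 2 (Weeks 12, 24): range; independent | k = 6 (Weeks 12 to 72): range; independent |
|---|---|---|
| 1% | 1–2%; 1.99% | 1–6%; 5.85% |
| 2% | 2–4%; 3.96% | 2–12%; 11.42% |
| 5% | 5–10%; 9.75% | 5–30%; 26.49% |
| 10% | 10–20%; 19.0% | 10–60%; 46.86% |

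For a planned arm of 280, p = 5% is 0.05 × 280 = 14 patients at a visit, compatible with 14 to 28 patients ever positive by Week 24.

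**4. An illustration matched in time.** Assume 15% ever positive over 72 weeks, 45% of onsets at Week 12 and 30% at Week 24, and a share t of cases transient, split evenly between one and two visits.

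- Ever positive by Week 24: 0.15 × (0.45 + 0.30) = 11.25%.
- Positive at Week 24: 0.15 × [0.30 + 0.45 × (1 − t/2)] = 10.2%, 9.6% and 8.9% for t = 0.3, 0.5 and 0.7.
- Gap: about 1.0, 1.7 and 2.4 percentage points.

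**5. Baseline positives in the denominator.** With x new positives, N samples and B baseline positives among them, the plan gives x/N and the at-risk figure is x/(N − B), a ratio of 1/(1 − B/N). If B/N is 1% to 10% (assumed), the ratio is 1/0.99 = 1.01 to 1/0.90 = 1.11.

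**6. Placebo background.** With a false-positive rate f per sample (assumed) and independent samples, the expected number of placebo patients ever positive at Weeks 12 and 24 is 280 × [1 − (1 − f)²]: 2.8, 5.6, 11.1 and 27.3 for f = 0.5%, 1%, 2% and 5%.

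**The case against.** A reader might infer that the trial will yield no ADA incidence at all. The documents do not support that. Results are recorded per patient, all are listed by period, and positive subjects are listed separately, so an any-time count can be derived. If *develop* means newly positive, the visit counts even add up to the cumulative numerator. What is missing is a planned and defined summary.

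A reader might also infer that there is no measure of assay background. That too goes beyond the text. Positivity before dosing is summarized in the eptinezumab arms, up to 560 samples; at an assumed 1% false-positive rate that is 0.01 × 560 = 5.6 expected positives. Only the concurrent background after Baseline is absent. Panel 2 shows that placebo blood is drawn, not that it is assayed; protocol 9.4.8 leaves the analysis to a separate protocol.

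It is tempting to say that Withdrawal Visit samples are lost. SAP 13.3.2 sits under the laboratory heading, and SAP 19.2.2 assigns withdrawal laboratory tests to nominal visits, so ADA may be covered. Protocol 11.1.3 lists ADA apart from safety laboratory data, and Panel 5 omits it. The point is unclear and needs one sentence in the SAP.

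Finally, these are descriptive safety summaries. They touch no hypothesis test, and a large bias has not been shown. That stands. It limits the weight of the point but does not supply the missing incidence.

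**Conclusion.** The point holds as a gap in the planned summaries. SAP 13.3.2 gives no per-patient incidence for an endpoint defined as development of ADA, its denominator includes patients not at risk, and it departs from the count-once practice used for PCS values and liver signals. Whether placebo patients who switch at Visit 8 are included in the Extension Period is not stated, and no concurrent placebo background is planned.

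The size cannot be fixed from the documents. On the visit-prevalence reading, with equal percentages across visits and complete sampling, any-time incidence is 1 to 2 times the visit figure over the Placebo-controlled Period and 1 to 6 times over the study; it equals the visit figure if positivity is persistent. On the inputs of the time-matched illustration, setting 15% ever positive over 72 weeks against a single-visit peak of 9% to 11% would suggest a gap of 4 to 6 points. That compares different time spans; at Week 24 the gap is about 1.0 to 2.4 points. Understatement is possible, not demonstrated, and its direction depends on how *develop* is read.

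The change should be made because it is cheap and the endpoint requires it. Efficacy inference and sample size are unaffected.

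**What to change.** Add to SAP 13.3.2 a once-per-patient treatment-emergent ADA incidence by treatment group and period:

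- **Numerator:** patients ADA-negative before first eptinezumab with any later positive sample, Withdrawal Visit samples included.
- **Denominator:** patients ADA-negative before first eptinezumab with at least one later sample.
- **Baseline-positive patients:** report separately, with boosted ADA if titres exist.
- **Placebo patients who switch:** include them in the Extension Period analysis, with the Visit 8 sample taken before infusion as their ADA baseline. Extension Period safety tables are already by treatment sequence, so they have their own columns.
- **By-visit table:** keep as support, and define *develop*. Define ADA-positive for the adverse event table in the same place.
- **Placebo column:** if placebo samples are assayed, show Weeks 0, 12 and 24 descriptively.

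The cost is SAP wording and one extra table, from eptinezumab samples already scheduled and results already to be listed. The placebo column costs nothing further only if those samples are assayed anyway. The downside is that the stated incidence may be somewhat higher than the by-visit percentages.

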- g Assessments involving interviews and scales must be done before the infusions. All efficacy and pharmacoeconomic assessments are PROs. PROs which are scheduled in alignment with a clinic visit can be completed in the clinic or in the remote setting within 3 days prior to the scheduled clinic visit date. Additionally, PGIC (at Week 4 only), HIT-6, EQ-5D-5L, HCRU, WPAI which are scheduled in alignment with a phone contact must be completed in the remote setting and can be completed on the day or within 3 days prior to the scheduled phone contact date.
- h The eDiary assessments will be completed in the remote setting on a daily basis.
- i At the Screening Visit, the patient must be assisted with the provisioning and training of the eDiary and training of efficacy and pharmacoeconomic assessments (PROs). Details will be provided in a separate user manual.
- j The eDiary closeout will take place at the Completion/Withdrawal Visit, while the patient is at site. Details will be provided in a separate user manual.

- k The patients will be contacted via phone every 4 weeks between infusion visits for eDiary compliance check, to ensure that selected assessments have been completed and for collection of relevant information such as AEs and concomitant medication.
- 1 PGIC at Week 4 must be completed in the remote setting.
- m At infusion visits, infusion related reactions (IRRs) must be checked as part of the overall AE collection, after infusion and before the patient is discharged from the site.
- n At infusion visits, physical examination, ECG, blood sampling (for clinical safety laboratory tests, ADA and biobank) and urine samples (for clinical safety laboratory tests and pregnancy) must be conducted before infusion. AEs, vital signs including body temperature should be checked before and after infusion.
- o The C-SSRS will be administered by the authorized rater at the clinic and prior to infusion.
- p Patients who test positive for ADA at the Completion Visit will be asked to provide up to two additional blood samples for immunogenicity testing at 12-week intervals for up to 24 weeks.
- q At infusion visits, patients must be monitored for a period of 1 hour from the end-of-infusion. Patients will be requested to stay longer should the investigator determine this is clinically warranted.

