5.4 Withdrawal Criteria

A patient must be withdrawn from the study if:

- the patient withdraws consent (defined as a patient who **explicitly** takes back their consent); section 8.9 states how the patient's data will be handled
- the patient has been randomized in error and has not received IMP
- the patient fails to comply with study procedures
- the patient is lost to follow-up (defined as a patient who fails to comply with scheduled study visits or contact, who has not actively withdrawn from the study, and for whom no alternative contact information is available [this implies that at least two documented attempts have been made to contact the patient])
- the investigator considers it, for safety, lack of efficacy, and/or study compliance reasons, in the best interests of the patient that he or she be withdrawn from treatment
- any site personnel break the randomization code for that patient
- the patient becomes pregnant
- the patient experiences an anaphylactic reaction or another severe and/or serious hypersensitivity reaction to the IMP infusion, as assessed by the investigator. If the event occurs during the IMP infusion, the infusion must be discontinued immediately
- the patient has a serum ALT or AST value >3 times the upper limit of the reference range and a serum total bilirubin value >2 times the upper limit of the reference range
- the patient has a serum ALT or AST value >5 times the upper limit of the reference range that is confirmed by testing <2 weeks later
- the patient has a QT_{cF} interval >500 ms; the decision to withdraw the patient may be postponed until a repeat ECG is taken, if it is taken within 24 hours
- the patient is at significant risk of suicide (defined as answering "yes" to suicidal ideation questions 4 or 5 or answering "yes" to suicidal behaviour on the C-SSRS at any time during the study)

Patients who withdraw will not be replaced.

6 Investigational Medicinal Product(s) (IMP(s))

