4.1 Definition of Periods

The study consists of the following periods:

- *Screening Period* (28-30 days): Starts at the Screening Visit and continues up to start of Visit 2 IMP infusion
- *Placebo-Controlled Period*: Starts at start of Visit 2 IMP infusion and continues up to start of Visit 8 IMP infusion
- *Extension Period*: Starts at start of Visit 8 IMP infusion and continues up to and including Visit 20

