13.1.4 Allocation of TEAEs to Treatment Periods

TEAEs will be allocated to treatment periods according to the time of onset of the adverse event:

- *TEAE in the Placebo-controlled Period* a TEAE that starts before the date and time of the start of Visit 8 IMP infusion
- *TEAE in the Extension Period* a TEAE that starts during or after administration of Visit 8 IMP infusion

For allocation of TEAEs to treatment periods, the same rule for imputed dates as specified above (in Section 13.1.3) applies, i.e. for incomplete start dates, only the imputed start date and not the time (which will not be imputed) of the adverse event will be taken into account in the allocation of the TEAE to periods.

If an adverse event starts on the day of the Visit 8 IMP infusion but with an unknown start time, the adverse event will be classified as treatment-emergent in the Placebo-controlled period.

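### The ADA-to-AE listings in SAP 13.3.2 split at the Visit 8 infusion, so a patient ADA-positive by the pre-infusion Visit 8 sample but never afterwards has Extension Period AEs, including a reaction to that infusion, in neither listing

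*SAP*

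**What the plan says.** Period boundary. SAP 4.1 defines the Extension Period thus: "Starts at start of Visit 8 IMP infusion and continues up to and including Visit 20". SAP 13.1.4 follows the same line: an Extension Period TEAE is "a TEAE that starts during or after administration of Visit 8 IMP infusion".

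Timing of the sample. Footnote n to Panel 2 of the protocol says that at infusion visits "blood sampling (for clinical safety laboratory tests, ADA and biobank) and urine samples (for clinical safety laboratory tests and pregnancy) must be conducted before infusion". The footnote n in SAP Appendix II agrees.

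CSR listing. SAP 13.3.2 will list "all the adverse events occurring before entering the Extension Period in patients with positive anti-eptinezumab antibody results in the Placebo-controlled Period"; it also takes in patients with antibodies already present at Baseline. ADA results and events are to be shown in date order.

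Addendum listing. The same section continues: "Similar listings will be provided for patients with ADA-positive results occurring after start of V8 IMP infusion". For the patients so selected, every adverse event is listed.

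Summary tables. SAP 13.3.2 also plans TEAE summaries for ADA-positive patients in each period. It does not say which samples make a patient ADA-positive for the Extension table.

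Withdrawal. Protocol 5.4 requires withdrawal if "the patient experiences an anaphylactic reaction or another severe and/or serious hypersensitivity reaction to the IMP infusion, as assessed by the investigator". Protocol 8.9 asks withdrawn patients to attend a visit 12 weeks after the last dose, and Panel 2 of the protocol schedules an ADA sample at that visit.

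**The concern.** The CSR listing restricts the events and the addendum listing restricts the patients, both at the same instant, and the Visit 8 sample is drawn just before it. A positive Visit 8 result therefore qualifies the patient for a listing that stops before the infusion. It does not qualify the patient for the listing that starts with it.

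A positive pre-dose sample followed by a reaction to that dose is a sequence that a date-ordered ADA-AE listing exists to show. At the first infusion the SAP does keep the link, because Baseline-positive patients are included in the CSR listing. There is no matching provision at Visit 8.

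The patients of most interest also have fewer chances to qualify later. Someone withdrawn after a hypersensitivity reaction at Visit 8 forgoes the scheduled samples at Visits 11, 14, 17 and 20 and has at most one later planned ADA sample.

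**Working it through.** The plan gives no figure to reproduce here, so the check applies the rules to a case. Take a patient randomized to eptinezumab who is ADA-positive in the pre-infusion Visit 8 sample and has an event that starts during or after that infusion.

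1. **Period of the ADA result.** The sample precedes the infusion (Panel 2, footnote n) and the Extension Period opens with the infusion (SAP 4.1). The result belongs to the Placebo-controlled Period.
2. **Period of the event.** It belongs to the Extension Period (SAP 13.1.4).
3. **CSR listing.** The patient is selected, but the event is left out because it starts after Extension entry.
4. **Addendum listing.** The patient is selected only if some ADA result after the start of the Visit 8 infusion is positive. If so, all the patient's events are listed, including the Visit 8 reaction.

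Step 4 depends on the later samples.

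- **Patient stays to completion.** There are four later scheduled samples (Visits 11, 14, 17, 20), each positive or negative: 2^4 = 16 patterns. Of these, 15 contain at least one positive and restore the patient to the addendum listing. One pattern (all negative) leaves the reaction in neither listing.
- **Patient is withdrawn after the Visit 8 infusion.** Only the Withdrawal Visit sample remains. Positive: listed. Negative: in neither listing. Missed: in neither listing.

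These are counts of logical patterns, not probabilities.

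The same reasoning covers a patient positive only at Baseline or only at Week 12: with no positive result after Visit 8, none of that patient's Extension events reaches either ADA-AE listing.

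Two readings would narrow the gap.

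- SAP 13.1.4 has an exception. "If an adverse event starts on the day of the Visit 8 IMP infusion but with an unknown start time", it is assigned to the Placebo-controlled Period and could reach the CSR listing. This helps only events with no recorded time.
- If a result is taken to occur when the laboratory reports it, rather than when the sample is drawn, a Visit 8 sample reported later might qualify. The SAP does not say this, and the listing itself is ordered by assessment date.

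On size, the number affected is (patients who enter the Extension Period) × (proportion positive by Visit 8) × (proportion of those with no later positive) × (proportion with an Extension event). The starting base is at most 2 × 280 = 560 patients, before dropout. The documents give none of the three proportions, so no count follows.

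**The case against.** The strongest reply is that nothing disappears. The addendum lists every event from Extension entry onward (SAP 13.1.5), tabulates events on dosing days with Visit 8 included (13.1.6), and lists events of special interest, with a repeat for hypersensitivity and anaphylaxis alone (13.1.11). AE listings carry the date and time of the latest infusion (13.1.1). All immunogenicity data and all positive subjects are listed by period (13.3.2), so the two halves can be joined by patient number. This is correct. A reader might infer that the reaction is absent from both reports, and the documents do not support that. Only the planned display that puts result and event side by side is lost.

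A reader might also infer that patients withdrawn for hypersensitivity have no further ADA sample. They have one planned, at the Withdrawal Visit, and a positive result there brings them back with all their events. What stands is that they have one chance in place of four, at a visit that protocol 8.9 asks for only where feasible. The optional sampling at the time of a reaction (protocol 10.6) covers histamine, tryptase, IgE and complement, not ADA.

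Nor do the documents show that the review is biased towards no signal. These outputs are descriptive, and the Extension TEAE summary for ADA-positive patients may count the event, since its window is undefined. A summary does not, however, show whether the positive result came before the event.

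Finally, selecting on within-period results is the SAP's general convention; the potentially clinically significant value listings in 13.2 split the same way. The convention fits ADA less well, because a pre-dose antibody result bears on the dose that follows. The inclusion of Baseline positives in the CSR listing already recognises this.

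**Conclusion.** The gap is real on the stated rules. A patient positive at or before the pre-infusion Visit 8 sample, with no positive afterwards because later samples are negative or the Withdrawal Visit sample is missed, has Extension Period events in neither ADA-AE listing. A reaction to the Visit 8 infusion is the clearest case. The consequence is a broken link between two items that are both reported, not missing safety data.

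The number of patients cannot be derived. Any count would rest on assumed rates of ADA positivity and loss of positivity, and would still need a rate of Extension events. The conclusion assumes that a result occurs on its sample date and that the event has a recorded start time. It is worth correcting because a stated selection rule leaves out cases that the linked display is meant to show.

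**What to change.** In SAP 13.3.2, select patients for the addendum ADA-AE listing on any ADA-positive result at any time up to the end of the study, including Baseline and the pre-infusion Visit 8 sample. List all their ADA results and all their adverse events in date order, so that each event can be read against the result before it. State the same definition of ADA-positive for the Extension Period TEAE summary, whose window is now undefined.

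This changes one selection rule and adds one definition, affecting two addendum outputs. No new samples or assays are needed. CSR outputs are unaffected, since SAP 2.1 schedules Extension outputs after the CSR is final. The downside is a longer listing that includes some patients whose positivity was early and transient; the dates make that visible.

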13.1 Adverse Events

13.1.1 General Methodology for Adverse Events

Unless otherwise specified, tables, graphs, and listings will be based on the APTS for the Placebo-controlled Period and the APTS_LT for the Extension Period.

All the tables and graphs will be presented by treatment group for the Placebo-controlled Period and by treatment sequence group for the Extension Period, unless otherwise specified.

Tables by preferred term and tables by system organ class (SOC) and preferred term will be sorted in descending order based on the percentages of patients with these adverse events in the eptinezumab 300 mg dose group.

Unless otherwise specified, the summaries of adverse events will include the number and percentage of patients with an adverse event. In tables displaying SOC or preferred terms, patients are counted only once within each SOC or preferred term.

Listings of adverse events will be sorted by site, treatment group, patient screening number, and adverse event start date, and include preferred term, investigator term, adverse event start date, the date of first IMP infusion, the date and time of the latest IMP infusion prior to the adverse event, the time since latest IMP infusion, duration of the adverse event, date of death, action taken, causality, intensity, seriousness, and outcome. For adverse events that change in intensity, each intensity will be included. In listings of adverse events, start or stop dates will be displayed as collected also in case of partially or completely missing dates.

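### SAP 13.3.2 leaves Extension adverse events in patients ADA-positive only up to Visit 8 out of both ADA-linked listings, and tabulates TEAEs for ADA-positive patients with no comparator

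*SAP*

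**What the plan says.** Timing comes first. Footnote n to Protocol Panel 2 puts ADA blood ahead of dosing at every infusion visit: "sampling (for clinical safety laboratory tests, ADA and biobank) and urine samples (for clinical safety laboratory tests and pregnancy) must be conducted before infusion". SAP 4.1 defines the Placebo-controlled Period thus: "Starts at start of Visit 2 IMP infusion and continues up to start of Visit 8 IMP infusion". SAP 13.1.4 defines an Extension TEAE as "a TEAE that starts during or after administration of Visit 8 IMP infusion".

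SAP 13.3.2 then plans three outputs that connect ADA to adverse events:

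- A listing for the CSR of "all the adverse events occurring before entering the Extension Period in patients with positive anti-eptinezumab antibody results in the Placebo-controlled Period", extended to patients who already had antibodies at Baseline.
- A listing for the addendum: "Similar listings will be provided for patients with ADA-positive results occurring after start of V8 IMP infusion". It shows all adverse events of the patients it admits.
- A table of TEAEs by SOC and preferred term, which "will be provided for the Placebo-controlled Period and for the Extension Period for patients who are ADA-positive".

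The AESI summaries in SAP 13.1.11 and the table of dosing-day TEAEs in SAP 13.1.6 cover all patients and are not split by ADA status. In SAP Appendix VI, Table 6, the infusion-related category requires a listed term plus onset on the dosing day after infusion start or, for some terms, also within the following 7 days. The hypersensitivity category has no timing criterion. SAP 13.1.1 sets the counting rule: "In tables displaying SOC or preferred terms, patients are counted only once within each SOC or preferred term".

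**The concern.** ADA development is a named safety endpoint, and the sponsor chose to link it to adverse events. A pre-infusion ADA result describes the patient's status at the infusion that follows. At Visit 8 the listing rules separate the two: the sample falls in one period and any reaction to the infusion in the next. A patient who is positive just before the Visit 8 infusion and reacts to it is a case that an ADA-linked listing should show.

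The scenario is realistic. Protocol 5.4 requires withdrawal after anaphylaxis or another severe or serious hypersensitivity reaction. Protocol 8.9 sets the Withdrawal Visit 12 weeks after the last dose, where the patient can attend. Such a patient has at most one further scheduled ADA sample, and so little chance to qualify for the addendum listing.

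The table raises a different problem. Event counts in ADA-positive patients mean little without the same counts in ADA-negative patients. The event types most relevant to ADA, hypersensitivity and infusion reactions, are not summarised by ADA status at all.

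**Working it through.** The plan states no figure to reproduce. The check applies its rules.

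**1. Place the sample and the event.** The Week 24 sample is drawn before the Visit 8 infusion, so by SAP 4.1 it belongs to the Placebo-controlled Period. A reaction with a known start time during or after that infusion belongs to the Extension Period by SAP 13.1.4.

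**2. Run every result pattern through the two listings.** Panel 2 schedules ADA samples at Visits 2, 5, 8, 11, 14, 17 and 20. The first three precede the Visit 8 infusion and the last four follow it. A missing sample is treated as not positive. There are 2^7 − 1 = 127 patterns with at least one positive.

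| Positive results | Patterns | CSR listing | Addendum listing | Visit 8 reaction shown |
|---|---|---|---|---|
| Up to Visit 8 only | 2^3 − 1 = 7 | Patient in, reaction after the cut-off | Patient not in | No |
| Up to Visit 8 and later | 7 × 15 = 105 | Patient in, reaction after the cut-off | Patient in, all events | Yes |
| Later only | 2^4 − 1 = 15 | Patient not in | Patient in, all events | Yes |

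The total is 7 + 105 + 15 = 127. In the 7 patterns of the first row, the reaction is in neither listing. The same holds for every other Extension event in those patients, across up to four infusions (Visits 8, 11, 14 and 17).

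**3. Exception.** SAP 13.1.4 assigns an event on the Visit 8 infusion day with unknown start time to the Placebo-controlled Period. If that rule carries over to the CSR listing, such an event is shown there and the count falls from 7 to 0 of 127. Protocol 10.3 asks for start and stop times for events shorter than 24 hours, so this should be uncommon.

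**4. What subtraction recovers from the tables.** The all-TEAE table in SAP 13.1.6 uses the same SOC and preferred-term layout. Eptinezumab patients in that table minus those in the ADA-positive table gives crude counts per preferred term for everyone not known to be positive. Small mismatches can arise because SAP 4.4 reports adverse events by actual treatment.

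**5. What subtraction does not recover.**

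- Timed infusion AESIs. The ADA table has no timing, and the tables that have timing have no ADA status. No subtraction gives both.
- Any-event totals by category. Take four ADA-positive patients, two counted under urticaria and two under pruritus (an illustration). If the events are in different patients, 4 patients have an event. If the same two patients have both, the total is 2. The table looks identical either way. The exception is a category with a single preferred term.

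**The case against.** The strongest reply is that nothing is hidden. A Visit 8 reaction appears in the listing of all Extension adverse events (SAP 13.1.5) and, where it qualifies, in the SAE, withdrawal, infusion-interruption, AESI and separate hypersensitivity listings. SAP 13.3.2 also lists all immunogenicity data and every positive patient by period. An ADA sample is scheduled at the Withdrawal Visit. No document makes an ADA-by-reaction comparison an objective, and grouping by ADA status at patient level is a defensible descriptive choice. All of this stands. It limits the consequence to matching patients by hand across listings. It does not close the gap in the listings that are meant to do that matching.

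Four stronger readings are tempting, and the documents do not support them:

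- A reader might infer that the Extension TEAE table also drops the Visit 8 reaction. The wording sets no period for the positive result, so read plainly a patient positive at Week 24 is in that table. Only the listing is affected.
- A reader might infer that events before the first positive sample are deliberately counted as events in positive patients. The SAP is silent on this, and the ADA listings are ordered by date, so the sequence is visible there.
- A reader might object to this rule: "Denominators for percentages will be the total number of samples taken for the specified visit". One ADA sample is scheduled per patient per visit, so the denominator is in effect patients tested.
- A reader might want a number of affected patients. The documents give no ADA incidence, persistence or reaction rate, so none can be derived.

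**Conclusion.** Both gaps hold as stated.

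The listing gap follows directly from the period definitions, the pre-infusion sampling and the two admission rules. It affects patients positive at Baseline, Week 12 or the Week 24 pre-infusion sample with no later positive result, whether later samples are negative or missing. For them, a Visit 8 reaction with a known start time and all later Extension events are outside both ADA-linked listings. The 7 of 127 patterns show which patients fall through, not how many.

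The table gap is one of presentation: no ADA-negative comparator, and no way to obtain timed infusion AESIs or any-event category totals by ADA status from the planned tables.

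The outputs are descriptive. Alpha, power and the primary endpoint are unaffected, and the events themselves are reported elsewhere. This is a change the sponsor could make with little effort, not one on which the trial's conclusions depend.

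**What to change.** 1. In SAP 13.3.2, extend the addendum listing to patients with any positive ADA result up to and including the Visit 8 pre-infusion sample, in addition to those positive afterwards. This is one sentence and closes the listing gap.

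2. Add an ADA-negative column to the TEAE table in SAP 13.3.2, and present the hypersensitivity and infusion AESI summaries of SAP 13.1.11 in the same way, by eptinezumab dose. Use patient denominators and show untested patients separately. Label the columns descriptive.

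3. Optionally, flag event onset relative to the first positive sample. Samples are 12 weeks (12 × 7 = 84 days) apart, so the date of seroconversion stays uncertain within that window.

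The cost is SAP wording and extra columns from data already collected. The downsides are small ADA-positive cells and a grouping formed after randomisation, so differences between columns cannot be read as effects of ADA.
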